8 STUDY PROCEDURES /EVALUATIONS

8.1 Study Procedures/Evaluations

- Medical history will be assessed by chart abstraction and confirmation with the patient at the Screening or Enrollment visit.
- Physical examination will include chart abstraction of height and weight and BMI and if not in chart will be performed at screening visit.
- Participants will be asked about hirsutism symptoms.
- Transvaginal ultrasound of uterus and ovaries will be performed to obtain the following measures: endometrial thickness and evaluation for presence of corpora lutea and number of corpora lutea.
- Urine pregnancy tests
- Participant Journal Logs will be used to track medication adherence, side effects, intercourse, and concomitant medications

Standard Clinical care:

- Transvaginal ultrasound will also be performed at the ongoing pregnancy visit to record the number of gestational sacs, measurement of gestational sac(s), yolk sac(s), crown rump length, presence of fetal heart motion and rate and any abnormalities.
- Assessment of tubal factor and uterine cavity by saline sonohystogram, hysterosalpingogram, or laparoscopy if recommended by provider however not required to participate in the study
- Semen analysis of male partner to rule out male factor
- 8.2 Medical record review will be performed for labs, including: TSH, prolactin, HbgA1c, 17-OH Progesterone, AMH, Rubella, FSH and estradiol, Total testosterone and SHBG; progesterone documenting anovulation. All of these labs are not required for participation but if they have been done should be documented. Documentation of TSH, HbgA1c and Rubella status recommended for participation. These will be entered into RedCap.

8.2.1 Clinical Laboratory Evaluations performed at local labs

- Progesterone will be assessed at the local lab to determine treatment plan for next cycle and ovulatory status
- Urine hCG will performed by the patient

• Serum hCG if indicated will be assessed at the local lab to confirm pregnancy status if positive urine hCG (standard clinical care)

9 ASSESSMENT OF SAFETY

9.1 Specification of Safety Parameters

9.1.1 Adverse Events

An adverse event is any untoward or unfavorable medical occurrence in a human subject, including any abnormal sign (for example, abnormal physical exam or laboratory finding), symptom, or disease, temporally associated with the subject's participation in the research, whether or not considered related to the subject's participation in the research.

9.1.2 Serious Adverse Events

SAEs are a subset of all AEs. A serious adverse event (SAE) is one that meets one or more of the following criteria:

- Results in death
- Is life-threatening (places the subject at immediate risk of death from the event as it occurred)
- Results in inpatient hospitalization or prolongation of existing hospitalization
- Results in a persistent or significant disability or incapacity
- Results in a congenital anomaly or birth defect
- An important medical event that may not result in death, be life threatening, or require hospitalization may be considered an SAE when, based upon appropriate medical judgment, the event may jeopardize the subject and may require medical or surgical intervention to prevent one of the outcomes listed in this definition.

9.2 Time Period and Frequency for Event Assessment and Follow-Up

Unanticipated problems will be recorded in the data collection system throughout the study.

The PI will record all reportable events with start dates occurring any time after informed consent is obtained until 7 (for non-serious AEs) or 30 days (for SAEs) after the last day of study participation. At each study visit, the investigator will inquire about the occurrence of AE/SAEs since the last visit. Events will be followed for outcome information until resolution or stabilization.

9.3 Characteristics of an Adverse Event

9.3.1 Relationship to Study Intervention

The Medical Monitors and the Study PI will assess the relationship of all adverse events to study intervention or study participation as either related or not related. Evaluation of relatedness will consider etiologies such as natural history of the underlying disease, concurrent illness, concomitant therapy, study-related procedures, accidents, and other external factors.

To assess relationship of an event to study intervention, the following guidelines will be used:

- 1. Related (Possible, Probable, Definite)
 - a. The event is known to occur with the study intervention.
 - b. There is a temporal relationship between the intervention and event onset.
 - c. The event abates when the intervention is discontinued.
 - d. The event reappears upon a re-challenge with the intervention.
- 2. Not Related (Unlikely, Not Related)
 - a. There is no temporal relationship between the intervention and event onset.
 - b. An alternate etiology has been established.

9.3.2 Expectedness of SAEs

The Medical Monitors and the Study PI will be responsible for determining whether an SAE is expected or unexpected. An adverse event will be considered unexpected if the nature, severity, or frequency of the event is not consistent with the risk information previously described for the intervention.

9.3.3 Severity of Event

The following scale will be used to grade adverse events:

- 1. Mild: no intervention required; no impact on activities of daily living (ADL)
- 2. Moderate: minimal, local, or non-invasive intervention indicated; moderate impact on ADL
- 3. Severe: significant symptoms requiring invasive intervention; subject needs major assistance with ADL

9.4 Reporting Procedures

Sites will report unanticipated problems (to subjects or others) in either the subjects REDCap record or via direct communication with the University of Iowa PI and study coordinator through email or phone call as needed. Alerts will be set up in REDCap, so that the University of Iowa study team is notified when an unanticipated problem is recorded.

Unanticipated problems will be reported to the IRB per institution reporting guidelines.

Adverse Events and Serious Adverse Events will be recorded in RedCAP, entry of Serious Adverse Events will trigger email notification to the PI and the study coordinator. Upon receipt of an adverse event alert, University of Iowa staff will follow up with the study site or subject who entered the data to trigger the alert to confirm accuracy. Data will be reported to the IRB of record and relying IRBs in accordance with institution policies. Additionally, reports of project safety data will be prepared for the safety monitors review twice annually.

10 STUDY OVERSIGHT

In addition to the PI's responsibility for oversight, study oversight will be under the direction of a safety monitors with expertise in Gynecology and in Reproductive Endocrinology and Infertility. The safety monitors will review safety data every 6 months. If safety concerns arise, more frequent reviews may be conducted.

Data reports will include side effect profiles and reports of any adverse events. We will also provide data on any multiple gestations.

11 CLINICAL SITE MONITORING

Throughout the study information and documents such as IRB approval memos, IRB approved materials, and study wide and site-specific amendments will be sent to relying sites via email and will be discussed with sites on monthly study conference calls. Information and documents from relying sites such as local context checklist, site delegation logs, changes in research personnel and information for continuing review will be sent to the University of lowa study coordinator via email and may be discussed on monthly conference calls.

All study data will be entered in REDCap by participating site staff. REDCap data quality functionality of field validation and queries will be used to identify and resolve discrepancies in data in real time. The REDCap report feature will be utilized by University of Iowa team to track completeness of data entry, any identified issues will be communicated to participating sites for confirmation and completion. REDCap provides a secure data entry platform which allows external collaborators to be added to projects, with data access groups to limit access to site specific records, while allowing all data to be entered into a single central project.

Protocol deviations can be assessed through both cycle information entered in standard data entry fields in subjects REDCap files or in a specified field for protocol deviations. REDCap data quality features will be used to flag deviations from study protocol related to timeframe of study events, dosing of study medication, and missing expected protocol events. Site staff will be contacted regarding these deviations to confirm accuracy of data entry and to determine if a deviation occurred. In addition to these fields, staff will be able to enter additional information on protocol deviations in a specific field in the subjects REDCap file. Data entered in this field will generate an alert to University of lowa Study staff to review the deviation.

Any concerns about noncompliance at participating sites will be discussed with that site's PI. University of lowa PI and study coordinator may request to review participating cites study records, including consent documents, in the event of concerns related to non-compliance. In the event non-compliance is found/or found to be a reasonable concern, the University of Iowa PI or designee will report the issue to the IRB of record. To resolve issues of non-compliance, staff training may be provided via memos or via conference call. Should retraining efforts not provide satisfactory resolution to noncompliance and/or violation of the contract/protocol, the site's participation in the study may be terminated.

11.1

12 STATISTICAL CONSIDERATIONS/DATA ANALYSIS

12.1 Justification of Effect Size

12.1.1 Prior Studies

Strong data on the per cycle cumulative ovulation with letrozole is available from the PPCOS II study. Unfortunately, there are not comparative quality data from randomized trials of the combination of letrozole and clomiphene citrate (CC), as discussed in the background section. The cumulative live birth proportion for subjects randomized to receive letrozole was 0.275 for the five-treatment cycle study period.

Per Cycle Ovulation and Live Birth Results in Letrozole arm of the PPCOS II study

	Ovulations/subject
Pre-treatment cycle 1	4/14 (28.6%)
Treatment cycle 1	178/360 (49.4%)
Treatment cycle 2	204/318 (64.2%)
Treatment cycle 3	179/268 (66.8%)

12.1.2 Minimum Clinically important differences

Considering the cumulative ovulation rates over 3 cycles from PPCOS II, data from our initial pilot study, as well as a clinically relevant increase in ovulation, we designed the study with 80% power to detect a 20% increase in ovulation rate among women treated with letrozole combined with CC, compared to those treated with letrozole monotherapy. We believe this method balances the risk of avoiding a type 2 error and along with an attainable sample size.

12.1.3 Significance Testing

Primary statistical analyses will invoke the intent-to-treat approach. Primary efficacy analysis will be performed by comparing the treatment groups with respect to the primary outcome of ovulation using Pearson chi-square test. Additional analysis will be performed using logistic regression modeling to adjust for other factors if needed such as the randomization stratification of study site, prior exposure to study medications, age and BMI. Summary descriptive statistics including mean, standard deviation, number of observations and quartiles will be provided for continuous variables; while frequencies and percentages will be provided for categorical variables. All hypothesis tests will be two-sided and all analyses will be performed using SPSS or SAS statistical software.

12.1.4 Sample Size Calculations

Considering the cumulative ovulation rate over 3 cycles from PPCOS II, data from our initial pilot study, and a clinically relevant increase in ovulation, we designed the study with 80% power to detect a 20% absolute difference in ovulation rate among women treated with letrozole combined with CC, compared to those treated with letrozole monotherapy. Allowing 10% dropout following randomization requires 92 patients per arm, or 184 total. Allowing for an additional 15-20% screening failure rate requires 220 consented to reach our randomization goal.

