trial of letrozole alone versus combination of letrozole and clomiphene citrate (CC) for up to 3 treatment cycles. Letrozole dosing will be increased in a stair-step fashion based on ovulation results. Participants will return for a mid-luteal ultrasound and progesterone lab to determine ovulatory status. Women will be randomized in a 1:1 ratio and the randomization scheme will be coordinated through the UIHC. Randomization will be stratified by site, age and BMI. The primary analysis will use an intent-to-treat approach to evaluate ovulatory rate in the

two treatment arms.

Objectives: To determine efficacy and safety of the combination letrozole and CC compared to letrozole alone in achieving ovulation in

infertile women with anovulation.

Primary Outcome: Ovulation will be the primary outcome determined by a mid-luteal progesterone level ≥ 3 and cumulative ovulation rate will be the primary efficacy parameter.

Secondary Outcome: Secondary efficacy parameters will include pregnancy rate (conception and clinical pregnancy), live birth rate, multiple gestation live birth rate, pregnancy loss rate (biochemical, miscarriage, ectopic) and time to pregnancy.

Side effect profile and complication rate will be monitored and reported.

Obstetric outcomes will include pregnancy complication rate, birth weight and sex, neonatal complication rate.

Ultrasound findings will be reported and compared between the two groups including: number of corpora lutea and endometrial thickness.

ClinicalTrials.gov Identifier

201906826

Population: 184 healthy women infertile women with polycystic ovary

syndrome or normogonadotropic normoestrogenic anovulation or oligo-ovulation, age \geq 18 to \leq 40. Additionally, the couple will

have no other major infertility factor.

Phase: IV

Number of Sites: 4 sites

University of Iowa Hospitals and Clinics Iowa City, IA with 2 ancillary sites

- Quad Cities Clinic, Davenport, IA
- Jordan Creek Clinic, Des Moines, IA

University of Wisconsin, Generations Clinic, Middleton, WI

Description Intervention:

of 184 women will be equally randomized to two different treatment arms at time of menses (spontaneous or induced with progestin withdrawal) or random start: A) letrozole 2.5 mg every day for 5 days (days 3-7 of cycle), or B) letrozole 2.5 mg and clomiphene citrate 50 mg every day for 5 days (days 3-7 of cycle), for a total of up to 3 treatment cycles.

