ovulation, with development of a dominant follicle in 82.9% of cycles (18). While it is possible that the difference between the two arms in our preliminary study could be explained by a dosing effect, the ovulation rate in our combination treatment group was higher than the 61.7% cumulative ovulation rate across five cycles of letrozole monotherapy with increasing doses up to 7.5 mg (4). Our finding of a similar ovulatory rate within the letrozole monotherapy arm to that previously reported suggests an additive effect of the combination of these medications.

0.286

Addition of CC to letrozole does not negatively impact ultrasound parameters: Data from our pilot study suggest among the subgroup who ovulated, endometrial thickness and number of follicles were similar across treatment arms (Table 1). This is reassuring in that CC is not having a negative impact on

the endometrium and multi follicular development appears limited.

Both a commentary (19), and Fertility and Sterility Live Global Journal Club praised our pilot study, but emphasized the need for additional

•	•	Letrozole + CC Group n=25	p value
# of follicles > 15 mm	0.5 (0-1)	1 (0-1.5)	0.081
Largest follicle size (mm)	15.5 (10.0-18.3)	17.0 (13.5-19.5)	0.228

 8.6 ± 3.9

 7.4 ± 2.3

Table 1. Ultrasound characteristics among patients who ovulated

studies to evaluate escalating dosages, multiple cycles, live birth, and multiple gestation with this novel combination treatment. Given our promising initial data, the goal is to expand on our pilot and conduct a trial with escalating doses of letrozole across three cycles of either letrozole monotherapy or combination therapy in 184 women. This will provide not only additional data on ovulation rates but provide essential information on side effects, multiple gestation rate and live birth rate which will better situate us completing a multicenter study evaluating live birth rate.

Endometrial lining (mm)

Significance and Innovation

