3.1.1 Primary Outcome Measure

The primary outcome measure is the occurrence of ovulation during the study period. Ovulation is defined as a mid-luteal progesterone level > 3 ng/mL. This will be tested 6-8 days following the patient reporting of an LH surge. If no LH surge is detected the lab will be drawn on cycle day 21-24. We will also analyze the ovulation rate of the follow up progesterone level.

We will utilize an intent-to-treat approach for the primary analysis of ovulation rate (utilizing the first progesterone level of each cycle) within the two treatment arms. If it is determined that timing of the initial progesterone level is inaccurate based on LH testing or patient symptoms, the progesterone test that is most clinically in line with accurate timing (6-8 days post LH surge) will be used. Ovulation rate will also be reported in those with a delayed response to treatment (needed repeat progesterone level due to anovulatory mid-luteal P4 level and follicle ≥ 14 mm). Patients will be analyzed according to the treatment group to which they are assigned, even if they did not receive the intended treatment or received only a portion of it. We will also perform a per protocol analysis to include only those patients who initiate treatment. Thus, those that are randomized but do not take the treatment due ineligibility will be excluded from the per protocol analysis. This per protocol analysis will provide data that is helpful to clinicians as it will include only those who initiated treatment.

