12.2 Statistical Analysis

All analyses will utilize the intention-to-treat (ITT) principle. All statistical tests of hypotheses will be two-sided. Baseline characteristics will be summarized by treatment arm. The primary outcome, cumulative ovulation, will be analyzed by comparing proportions utilizing a chi square test with significance set at 0.05. Dichotomous secondary outcomes will be analyzed in the same manner as the primary outcome. Two-sided t-tests will be used to compare endometrial lining thickness. Wilcoxon-Mann-Whitney tests will be used to compare number of corpora lutea. Time to pregnancy will be analyzed as a continuous variable using Kaplan-Meier survival analysis. Per-protocol analyses will be conducted to provide additional insight.

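### Is 80% power for a 20-point difference unsupported because no ovulation rate is stated for either arm?

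*Combined protocol and SAP*

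**What the plan says.** Section 12.1.4 designs the trial for "80% power to detect a 20% absolute difference in ovulation rate", allows 10% dropout, and randomises 92 women per arm (184 in total). Section 12.1.2 makes nearly the same statement, "80% power to detect a 20% increase in ovulation rate", without the word absolute. Both sections say that they considered a three-cycle cumulative rate from the earlier letrozole trial (PPCOS II) and the pilot study. Neither gives the rate assumed in either arm.

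Section 12.1.1 introduces the evidence as follows: "Strong data on the per cycle cumulative ovulation with letrozole is available from the PPCOS II study". Its table then lists ovulation in each cycle separately: 178/360, 204/318 and 179/268. Section 2.1 gives a "61.7% cumulative ovulation rate across five cycles of letrozole monotherapy", and single-cycle pilot rates of 77% and 43%.

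On the outcome, the Protocol Summary says "cumulative ovulation rate will be the primary efficacy parameter". Section 3.1.1 says "The primary outcome measure is the occurrence of ovulation during the study period", and also describes the "primary analysis of ovulation rate (utilizing the first progesterone level of each cycle"). Section 12.2 says: "The primary outcome, cumulative ovulation, will be analyzed by comparing proportions utilizing a chi square test with significance set at 0.05".

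**The concern.** The number of women needed to detect a fixed difference between two proportions depends on where the control proportion lies. With only the difference stated, the calculation cannot be repeated from the plan's own inputs.

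There may also be a mismatch of units. The average of the tabulated by-cycle proportions is close to 60%, the control rate that returns 92 per arm. The primary outcome, however, appears to be whether a woman ovulates at least once in up to three cycles. With three chances, and letrozole increased after an anovulatory cycle, that rate could be well above the by-cycle average. If it exceeded 80%, a 20-point gain could not occur and the headline power statement would describe an impossible effect. If it were well below 60%, the trial would be somewhat underpowered. Either way, a reader could be unsure what effect the trial was built to find.

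**Working it through.** **Inputs.** Two-sided 5% level (12.2), 80% power, 20-point absolute difference and 10% dropout (12.1.4), 1:1 allocation (Protocol Summary). The control rate p1 is not stated, so it is treated as an assumption and varied.

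**Reproducing 92 per arm.** The usual pooled-variance formula, with p̄ = (p1 + p2)/2, is

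n = [1.960 √(2p̄(1 − p̄)) + 0.842 √(p1(1 − p1) + p2(1 − p2))]² / (p2 − p1)²

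At 60% versus 80%, p̄ = 0.70:

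- first term: 1.960 × √0.42 = 1.270
- second term: 0.842 × √0.40 = 0.532
- n = (1.270 + 0.532)² / 0.04 = 3.249 / 0.04 = 81.2, so 82 evaluable per arm
- with 10% dropout: 82 / 0.9 = 91.1, so 92 randomised per arm

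This is the plan's figure exactly. That the sponsor used 60% is an inference.

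**What the documents say about the control rate.**

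- Pooled over cycles 1 to 3: (178 + 204 + 179) / (360 + 318 + 268) = 561/946 = 59.3%.
- Lowest possible per-woman rate over three cycles in that trial: the 204 women who ovulated in cycle 2, out of the 360 treated in cycle 1, give 56.7%.
- If cycles were independent: 1 − (182/360)(114/318)(89/268) = 94.0%. This is an illustration only, since cycles in the same woman are correlated.
- The five-cycle figure is 61.7%. If it is per woman, the three-cycle rate in the same trial cannot exceed it, so that rate lies between 56.7% and 61.7% and 60% is well supported. If it is pooled over cycles, the sponsor is using cumulative in the pooled sense, and the matching three-cycle figure is the 59.3% above. The documents do not settle which.

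**Sensitivity with 82 evaluable per arm (same approximation).**

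| Control rate | Power for +20 points | Difference detectable with 80% power |
|---|---|---|
| 50% | 75% | 21.2 points |
| 56.7% | 78% | 20.4 points |
| 60% | 80% | 19.9 points |
| 61.7% | 82% | 19.6 points |
| 70% | 90% | 17.7 points |
| 80% | at the ceiling | 14.5 points |
| 85% | not attainable | 12.3 points |
| 90% | not attainable | 9.6 points |

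**Absolute or relative.** A relative 20% increase from 60% would be 60% versus 72%, which needs 244 evaluable and 272 randomised per arm. With 92 per arm, and the word absolute in 12.1.4, the shorter wording in 12.1.2 is a clerical slip.

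**Unit of analysis.** The Protocol Summary, 3.1.1 and 12.2 all describe a cumulative outcome or its occurrence over the study, compared as simple proportions. Section 12.3.3 reserves generalized estimating equations for repeated observations within a woman, in secondary analyses. The phrase in 3.1.1 about the first progesterone of each cycle can be read as saying which blood sample counts when a cycle has two. On that reading it is consistent with one yes-or-no result per woman.

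**The case for a change.** The strongest opposing case is that the source named for the design, a three-cycle cumulative rate, appears nowhere as a number, and that 60% can only be recovered by working backwards. Per-woman rates should normally exceed by-cycle rates. In a simple beta-binomial model with a 59.3% chance per cycle, a three-cycle rate of only 60% needs a within-woman correlation of about 0.98. On that view the 20-point target may rest on the wrong quantity, and a few added sentences would cost nothing.

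The omission is real, and the documents do not prove that 60% was meant per woman. The implausibility argument is weaker. The model holds the rate constant over three cycles for every woman, whereas the table shows it rising from 49.4% to 66.8% while the denominator falls from 360 to 268. It also sets aside the 61.7% figure, which would cap the rate if it is per woman. Even if the control rate is higher than 60%, the error favours the trial, because smaller differences become detectable.

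Two further points do not add to the case. The 220 women to be consented imply 1 − 184/220 = 16.4% screen failure, inside the stated 15–20%. If every dropout were counted as non-ovulatory, 60% versus 80% would become 54% versus 72% with 92 per arm, and power would be about 72%. That belongs to the missing-data rule in 12.4, which names both a conservative and a liberal option, and not to the missing control rate.

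**Conclusion.** No change follows. The assumed rates are missing from 12.1.2 and 12.1.4, but no stated number is shown to be wrong. The figure of 92 per arm is reproduced exactly at 60% versus 80%, close to every multi-cycle letrozole average in the documents (59.3% pooled over three cycles, 61.7% over five). Across control rates from 57% to 70%, power for 20 points runs from 78% to 90%, so the largest shortfall in that range is about 2 points. Above 80%, where 20 points cannot be reached, differences of about 14.5 down to 9.6 points remain detectable up to a 90% control rate.

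Followed as written, the trial compares cumulative ovulation between 184 randomised women by chi-square and reaches a sound conclusion. What a null result argues against will be judged from the observed rates and the confidence interval for their difference, not from the planning rate.

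This rests on three assumptions: that the primary comparison uses one result per woman, that about 82 women per arm are evaluable, and that the control rate is not far below 57%. The 57% is a floor for the earlier trial and not for this one; at 50%, power would be 75%.
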